**Panel 2: Secondary and exploratory objectives and endpoints**

Objectives	Statistical approach	Estimand				Endpoints
Secondary objective		Estimand type	Interpretation	Intercurrent events and strategy	Population level summary	Secondary endpoint 
To evaluate the safety of twice-daily applications of delgocitinib cream 20 mg/g in the treatment of adolescents with moderate to severe CHE.	Not applicable	Not applicable	Not applicable	Not applicable	Not applicable	• Number of treatment-emergent  AEs from baseline up to Week 18  .

Objectives	Statistical approach	Estimand				Endpoints
Exploratory objectives		Estimand type	Interpretation	Intercurrent events and strategy	Population level summary	Exploratory endpoints
To evaluate the health-related quality of life and efficacy of twice-daily applications of delgocitinib cream 20 mg/g compared with cream vehicle in the treatment of adolescents with moderate to severe CHE over time.	Frequentist.	Primary.	Response achieved without IEs.	Composite strategy:  Initiation of rescue treatment, permanent discontinuation of IMP.	Risk difference.	Efficacy 
 
• HECSI-90 at Weeks 4 and 8.
 
• HECSI-75 at Weeks 4, 8, and 16.
 
 Health-related quality of life and efficacy 
 
• Reduction of HESD itch score (weekly average) of <math>\geq 4</math> points from baseline at Weeks 2, 4, and 8.
 
• Reduction of HESD itch score (weekly average) of <math>\geq 3</math> points from baseline at Weeks 2, 4, 8, and 16.
 
• Reduction of HESD pain score (weekly average) of <math>\geq 4</math> points from baseline at Weeks 2, 4, and 8.
 
• Reduction of HESD pain score (weekly average) of <math>\geq 3</math> points from baseline at Weeks 2, 4, 8, and 16.
 
• Reduction of HESD score (weekly average) of <math>\geq 4</math> points from baseline at Weeks 2, 4, and 8.
 
• Reduction of HESD score (weekly average) of <math>\geq 3</math> points from baseline at Weeks 2, 4, 8, and 16.
 

Objectives	Statistical approach	Estimand				Endpoints
					Difference in mean change (or percentage change)	Efficacy 
 
• Percentage change in HECSI score from baseline to Weeks 4, 8, and 16.
 
 Health-related quality of life and efficacy 
 
• Change in HESD itch score (weekly average) from baseline to Weeks 2, 4, 8, and 16.
 
• Change in HESD pain score (weekly average) from baseline to Weeks 2, 4, 8, and 16.
 
• Change in HESD score (weekly average) from baseline to Weeks 2, 4, 8, and 16.
 
• Change in cDLQI score from baseline to Week 4.
 

- 1) In addition to the secondary safety endpoint listed, clinical laboratory tests, vital signs, and physical examination at screening and end of treatment; use of rescue treatment; and subjects' assessment of local tolerability will be evaluated.
- 2) An event will be considered treatment emergent if started after the first application of IMP or if started before the first application of IMP and worsened in severity after first dose of IMP.
- 3) Among subjects with a baseline HESD itch score (weekly average)  $\geq 4$  points.
- 4) Among subjects with a baseline HESD itch score (weekly average)  $\geq 3$  points.
- 5) Among subjects with a baseline HESD pain score (weekly average)  $\geq 4$  points.
- 6) Among subjects with a baseline HESD pain score (weekly average)  $\geq 3$  points.
- 7) Among subjects with a baseline HESD score (weekly average)  $\geq 4$  points.
- 8) Among subjects with a baseline HESD score (weekly average)  $\geq 3$  points.
- 9) 'Number of treatment-emergent AEs from baseline up to Week 18' will be analysed descriptively according to the specifications in section 5.8.1.

[figure not shown]
**Abbreviations:** AE = adverse event; cDLQI = Children's Dermatology Life Quality Index; CHE = chronic hand eczema; HECSI = Hand Eczema Severity Index; HECSI-75 = at least 75% improvement in HECSI score from baseline; HECSI-90 = at least 90% improvement in HECSI score from baseline; HESD = Hand Eczema Symptom Diary®.

## 1.2 Trial design

This trial is a phase 3, randomised, double-blind, vehicle-controlled, parallel-group, multi-site trial. The trial is designed to evaluate the efficacy and safety of delgocitinib cream 20 mg/g applied twice-daily for 16 weeks in adolescents 12-17 years of age with moderate to severe chronic hand eczema. The trial design is illustrated in [Panel 3](#).

### Panel 3: Trial design

\* For subjects using treatments that are listed as exclusion criteria, the duration of the screening period will depend on the required wash-out period. In view of a 28-day wash-out for some of these treatments and the allowed visit window (+3 days), the screening period can be extended up to 31 days.

**Abbreviations:** d = day; IGA-CHE = Investigator's Global Assessment for chronic hand eczema®; N = number of subjects; w = week.

### Protocol amendment

The original protocol was dated 13-Jan-2022. The amendment was considered substantial and was mainly written to change the statistical methodology to a Bayesian analysis, where data from the adult population from recently completed pivotal phase 3 trials (LP0133-1401 and LP0133-1402) will be leveraged to analyse efficacy endpoints in the adolescent population. The change in the statistical methodology was done as LEO Pharma believes that, based on results from the completed clinical development program for delgocitinib, there is sufficient

THIS DOCUMENT CONTAINS CONFIDENTIAL INFORMATION AND MUST NOT BE COPIED OR MADE AVAILABLE TO ANY THIRD PARTY WITHOUT THE PRIOR WRITTEN CONSENT OF THE LEO PHARMA GROUP

understanding of CHE pathophysiology and the pharmacology of delgocitinib to support using efficacy results from the adult trials as prior information to the Bayesian analysis of the adolescent data.

## 2 Testing strategy

### 2.1 Testing hierarchy and statistical hypothesis

The Bayesian analyses of the primary estimand for the primary and key secondary endpoints are considered the confirmatory evidence for the trial.

The treatment effect (defined as proportion of responders for delgocitinib cream 20 mg/g minus the proportion of responders for cream vehicle) for all the binary confirmatory endpoints will be evaluated based on the calculated difference of posterior distributions for delgocitinib cream 20 mg/g and cream vehicle.

[figure not shown]
Delgocitinib cream 20 mg/g is considered superior to cream vehicle if the 2.5% percentile of the posterior distribution of the treatment difference is  $\geq 0$ .

Hierarchical evaluation, which is applied for the Bayesian analyses, will be used to control the overall type I error at a nominal one sided 2.5% level. This is built on the principle that the IGA-CHE TS superiority at Week 16 will have to be established before sequential testing for additional benefits (key secondary endpoints) related to efficacy.

If superiority is claimed for the primary endpoint, then evaluation of the next endpoints will be done in a fixed sequential order as specified in [Panel 4](#). This process will be repeated until no further tests are significant.

Only analyses based on the Bayesian approach will be part of the testing hierarchy.

**Panel 4: Graphical display of the testing procedure for primary and secondary endpoints**

\* From baseline in subjects with baseline ≥ threshold of response

† Average score of 6 symptom items, i.e., itch, pain, cracking of the skin, redness, dryness, and flaking

**Abbreviations:** HECSI-90 = at least 90% improvement in HECSI score from baseline; HESD = Hand Eczema Symptom Diary®; IGA-CHE = Investigator's Global Assessment for chronic hand eczema®; IGA-CHE TS = IGA-CHE treatment success, i.e. an IGA-CHE score of 0 (clear) or 1 (almost clear) with a ≥2-step improvement from baseline.

### 3 Sample size

Sample size documentation is provided in the CTP Section 14.1.

### 4 Trial analysis sets

For the purposes of analysis, the analysis sets presented in [Panel 5](#) are defined.

**Panel 5: Trial analysis sets**

Trial analysis set	Description
FAS	

All randomised to treatment and exposed subjects. Subjects will be included in the analyses according to the planned treatment.

SAF	

All subjects who are exposed to IMP. Subjects will be included in the analyses according to the treatment they actually received.

**Abbreviations:** FAS = full analysis set, IMP = investigational medicinal product, SAF = safety analysis set.

The FAS is used to analyse endpoints related to the efficacy objectives, and the SAF is used to analyse the endpoints and assessments related to safety.

For analyses of safety all subjects who have had at least one application with delgocitinib 20 mg/g will be analysed in the delgocitinib 20 mg/g treatment group. This is done to ensure that no drug reactions to delgocitinib 20 mg/g treatment will erroneously be assigned to the vehicle treatment group.

THIS DOCUMENT CONTAINS CONFIDENTIAL INFORMATION AND MUST NOT BE COPIED OR MADE AVAILABLE TO ANY THIRD PARTY WITHOUT THE PRIOR WRITTEN CONSENT OF THE LEO PHARMA GROUP

Exclusions from the FAS can be considered in special cases as described in ICH E9, Section 5.2.1., Full Analysis Set. If it is decided to exclude a randomized subject from the FAS, a justification addressing ICH E9 will be given in the Classification Brief before breaking the randomization code.

## **5 Statistical analysis**

### **5.1 General principles**

All frequentist significance tests will be one-sided using the 2.5% significance level. Operationally, the one-sided (superiority) hypotheses will be evaluated by deriving the two-sided p value; the null hypothesis will be rejected if the p value is smaller than 5% and if the point estimate is in favor of the alternative hypothesis.

All confidence intervals will be presented with 95% degree of confidence, unless otherwise specified.

An observed-cases approach will be used for tabulations of data by visit (that is, involving only those subjects who attended each specific visit).

Categorical data will be summarised using the number and percentage of subjects in each category and treatment group. Continuous data will be summarised using the mean, median, SD, 1st quartile, 3rd quartile, minimum, and maximum values.

Baseline measurements will be defined as the latest available observation at or prior to the date of randomization. Subjects without a baseline measurement for a given efficacy score will be excluded from the corresponding analysis.

In case of randomization in wrong stratum with respect to baseline IGA-CHE score, the statistical analyses will use the baseline IGA-CHE score confirmed by the investigator in the eCRF. This is due to the fact that the disease severity according to baseline IGA-CHE score is considered to be a strong prognostic factor for the treatment effect.

Simulation seed used for MI will be 1331426 for both types of imputation (MI based on MAR and MI based on Bernoulli distribution).

## 5.1.1 Handling of missing values

### 5.1.1.1 Multiple imputation

#### 5.1.1.1.1 Multiple imputation based on missing at random assumption (MAR)

Multiple imputation will only be performed for the primary endpoint.

For the treatment policy estimands' analyses the MI method includes the use of the FCS method assuming MAR to impute missing data. When analyses require MI procedures of data, 100 complete datasets will be generated.

MI under the MAR assumption will be performed using PROC MI in SAS with the FCS method 'logistics' for arbitrary missing patterns (1). Section 7.2 provides an example of SAS code to perform MI.

When analyses require MI procedures of data, the multiple-imputed datasets will be created in the following way:

1. A dataset will be created with longitudinal data in wide format (one row per patient).
2. For each timepoint missing (weeks 2, 4, 8, 12 and 16) values will be imputed using PROC MI within treatment group for IGA-CHE. The regression model for a certain timepoint will include the 2 preceding and 2 subsequent timepoints as predictors, in addition to baseline IGA-CHE score. Exceptions being the first 2 and last 2 timepoints, where the number of previous and subsequent timepoints are reduced to zero or one.
3. IGA-CHE TS is derived based on the imputed score for each of the 100 datasets and will be derived from imputation of the underlying ordinal score.
4. The relevant model is fitted for the 100 complete datasets, and Rubin's rule is applied, in order to derive the estimated treatment difference, associated SE and CI.

If there are no between-imputation variance, i.e., all the 100 imputed datasets are identical, it will not be feasible to estimate the variance using Rubin's rule for MI. Instead, the first imputed dataset will be used for analysis.

For imputation of IGA-CHE scores, it may occur that the observed data from which the imputation model is fitted does not contain all categories of the IGA-CHE predictors necessary for the imputation. For example, if all subjects with an IGA-CHE score of 3 at Week 12 have missing data at Week 16, then a regression model based on Week 12 data cannot predict the Week 16 outcome in those subjects, unless the IGA-CHE score of 3 at Week 12 is combined with other IGA-CHE scores. To avoid this situation, in this example

THIS DOCUMENT CONTAINS CONFIDENTIAL INFORMATION AND MUST NOT BE COPIED OR MADE AVAILABLE TO ANY THIRD PARTY WITHOUT THE PRIOR WRITTEN CONSENT OF THE LEO PHARMA GROUP

IGA-CHE scores of 2 and 3 at Week 12 will be combined into a single category for the purpose of the imputation.

If this situation arises, IGA-CHE categories will be combined into a single category at the specific visit for the purpose of the specific imputation, according to the rules in [Panel 6](#).

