## 10 Discontinuation and withdrawal

### 10.1 General principles

A subject may withdraw from the trial (prior to first dose or during the treatment period) or permanently discontinue trial treatment at any time if the subject, the parent/guardian, the investigator, or LEO Pharma considers that it is not in the subject's best interest to continue.

If a subject permanently discontinues IMP, the subject will be asked to attend an early termination visit, the primary endpoint visit, and the safety follow-up visit. If a subject or the subject's parent/guardian do not agree to attend these visits, the subject withdraws from the trial. To obtain a comprehensive efficacy evaluation of delgocitinib, it is of importance to assess the efficacy for each subject at the planned primary endpoint visit at Week 16.

Subjects who withdraw from the trial and subjects who permanently discontinue IMP will not be replaced.

If a subject withdraws from the trial, the subject or the subject's parent/guardian may request destruction of any samples taken and not tested, and the investigator must document this in the subject's medical record.

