### 14.1 Sample size

92 subjects will be randomised 3:1 to delgocitinib cream 20 mg/g or cream vehicle.

Based on response rates from the phase 2b dose-ranging trial in adults (LP0133-1273), a one-sided significance level at 2.5% and a sample size of 92 subjects will provide at least 80% power for detecting a treatment difference in the primary endpoint assuming an IGA-CHE TS response at Week 16 of 40.2% for delgocitinib cream 20 mg/g and 10.5% for cream vehicle.

When the response rates from LP0133-1401 and LP0133-1402 are included in the sample size calculation, this will result in a power which is lower than first anticipated.

The power obtained when using the Bayesian approach on a sample size of 92 subjects is explained in Section [14.3.17](#).

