#### 14.3.17.2 Evaluation of design characteristics (type I error, power and bias) for the Bayesian analysis of the primary endpoint

The between-trial heterogeneity for the primary endpoint IGA-CHE TS is set to  $\tau = 0.5$ , the weight on the non-informative part of the prior is set to 0.2 (20%).

This ensures a type I error <5% for efficacy rates <10% (average observed efficacy rates for cream vehicle was 8.4% in the adult trials LP0133-1401 and LP0133-1402) and a high power (>75%) for efficacy levels above observed efficacy levels (average difference in adult trials is 15.9%).

In the following sections, the selection of the parameters for the primary endpoint IGA-CHE TS are justified and discussed.

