### 5.6.1 Supplementary estimand for binary primary endpoint: treatment policy strategy, Frequentist approach

The supplementary estimand “Treatment policy” evaluates the treatment effect in adolescents 12-17 years of age with moderate to severe CHE as the risk difference for achieving a response, regardless of initiation of rescue treatment or permanent discontinuation of IMP.

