### 7.2 Appendix 2: SAS- and R-code

#### 7.2.1 SAS code for multiple imputation

```
proc mi data = inddata nimpute = 100 out = uddata seed = 1331426;
  where trt01pn=treatment;
  class w0 w30 w40 w50 w60 w70;
  var w0 w30 w40 w50 w60 w70;
  fcs logistic(W30 = W0 W40 W50 / likelihood=augment);
  fcs logistic(W40 = W0 W30 W50 W60 / likelihood=augment);
  fcs logistic(W50 = W0 W30 W40 W60 W70 / likelihood=augment);
  fcs logistic(W60 = W0 W40 W50 W70 / likelihood=augment);
  fcs logistic(W70 = W0 W50 w60 / likelihood=augment);
run;
```

THIS DOCUMENT CONTAINS CONFIDENTIAL INFORMATION AND MUST NOT BE COPIED OR MADE AVAILABLE TO ANY THIRD PARTY WITHOUT THE PRIOR WRITTEN CONSENT OF THE LEO PHARMA GROUP

where IGA-CHE score at baseline (Week 0) is contained in the variable IGABL, the score of the variable of interest at Week 1 is contained in the variable w1, and similarly for other visits.

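### The treatment-policy imputation uses neither the early termination IGA-CHE nor off-IMP status, so stoppers who also miss Week 16 are imputed mainly from on-treatment subjects

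*SAP*

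**What the plan says.** - **Estimand.** SAP 5.6.1 defines the supplementary estimand as the risk difference in response "regardless of initiation of rescue treatment or permanent discontinuation of IMP". SAP 5.6.1.2 uses observed data after the intercurrent event and imputes missing Week 16 values by multiple imputation under MAR within treatment group.
- **Visits after stopping.** Under Protocol 10.1, when IMP is permanently stopped, "the subject will be asked to attend an early termination visit, the primary endpoint visit, and the safety follow-up visit". Protocol 10.3 lists the same three visits. Panel 2 marks IGA-CHE at early termination and at the Week 16 primary endpoint visit; the follow-up is by phone unless a site visit is needed.
- **Imputation model.** SAP 5.1.1.1.1: "For each timepoint missing (weeks 2, 4, 8, 12 and 16) values will be imputed using PROC MI within treatment group for IGA-CHE". The predictors are baseline IGA-CHE and up to two scheduled visits on each side. The variable list in SAP 7.2.1 is "var w0 w30 w40 w50 w60 w70", and the Week 16 model there uses baseline, Week 8 and Week 12.
- **Sensitivity analysis.** SAP 5.6.1.3 sets missing Week 16 values to non-response.

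**The concern.** The rating made when a subject stops IMP is the most recent information on severity. It is collected, but the written model has no place for it. The model also cannot tell a subject who is off IMP from one who is on it.

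Protocol 5.3 says that these events are most often due to lack of efficacy or to treatment features the subject finds unacceptable. MAR is hard to defend for such subjects if severity at the stop is left out. At stake is the main estimate for the treatment-policy estimand: missing stoppers receive roughly their arm's on-treatment response, which helps the arm where that response is higher.

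**Working it through.** **1. Plan figures.** The documents give no discontinuation rate and no figure for this bias. The nearest stated figure is the power in Protocol 14.1: "a one-sided significance level at 2.5% and a sample size of 92 subjects will provide at least 80% power", "assuming an IGA-CHE TS response at Week 16 of 40.2% for delgocitinib cream 20 mg/g and 10.5% for cream vehicle". A pooled-variance z-test with 69 and 23 subjects gives 80.7%, so it reproduces. Nothing below rests on it except the arm sizes.

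**2. One subject traced.** A subject stops at Week 5, attends early termination and misses Week 16. Weeks 8 and 12 are unobserved because those visits are no longer asked for. The Week 16 model needs exactly those two values, so both are imputed first, mostly from subjects still on IMP. The early termination rating enters nowhere.

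**3. Arithmetic.**
- Inputs: on-drug response of 24.3% and 8.4% (Protocol Panel 21). Assumed: q, the share of the arm that stops and misses Week 16, and p_off, their true Week 16 response.
- Bias per arm = q × (p_on − p_off), if the draws follow the on-drug rate.
- With equal q and equal p_off in both arms, p_off cancels: bias in the risk difference = q × (24.3 − 8.4) = q × 15.9 points.

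| q per arm | Bias in risk difference |
|---|---|
| 5% | 0.8 points |
| 10% | 1.6 points |
| 20% | 3.2 points |

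- Unequal case: q = 5% on delgocitinib and 15% on vehicle, p_off = 0: 0.05 × 24.3 − 0.15 × 8.4 = 1.2 − 1.3, about zero.
- At the phase 2b rates used for sizing, the multiplier is 40.2 − 10.5 = 29.7, giving 1.5 points at 5% and 3.0 at 10%. Protocol 14.1 itself accepts that the phase 3 rates lower the power.

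**4. Simulation.** 400,000 IGA-CHE paths per arm, with assumed transition, stopping and return rates. Completer response was about 26% and 11%. Imputation was within arm, from baseline and the two preceding scheduled visits, which simplifies the SAP's chained equations. The last column enters the early termination rating no later than Week 12.

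| Stop IMP | Stoppers returning at Week 16 | Bias in risk difference, model as written | Bias with early termination rating |
|---|---|---|---|
| about 10% | none | 0.87 points | 0.72 |
| about 10% | half | 0.41 | 0.33 |
| about 18% | none | 1.82 | 1.43 |
| about 18% | half | 0.87 | 0.67 |

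Missing delgocitinib stoppers had a simulated true response of 10%. The model as written drew 24 to 26%, and 20 to 21% with the early termination rating added. The rating removes 27 to 30% of the bias in the delgocitinib arm. In the risk difference it removes 18 to 23%, because the vehicle bias falls too.

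**5. Scale.** The standard error of the risk difference at 24.3% and 8.4% is √(0.243 × 0.757/69 + 0.084 × 0.916/23) = 0.078, or 7.8 points. A bias of 1.6 points is about 0.2 standard errors.

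**The case against.** Four stronger readings are tempting, and the documents do not support them.

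- A reader might infer that IGA-CHE follow-up ends when IMP stops. It does not: Week 16 is kept for stoppers, and only those who also miss it are affected.
- A reader might infer that these subjects are imputed literally as if on treatment. Off-drug Week 16 values that are observed enter the within-arm fit. They are simply not distinguished from on-drug values.
- A reader might infer that the early termination rating is certainly discarded. SAP section 1 places derivation rules in the ADRG and define.xml, which are not available here, and SAP 5.1.1.1.1 calls the code an example. A mapping could exist. However, SAP section 1 also says its detail should let a reader reproduce the analyses, and the imputation steps mention no such rule.
- A reader might infer that the trial's conclusion is at risk. Only Bayesian analyses are in the testing hierarchy (SAP 2.1), and they count intercurrent events and missing data as non-response (SAP Panel 8).

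It can also be said that the non-response analysis already covers the problem. In part it does: if p_off is 0 to 5% and q is 10%, it understates each arm by only 0 to 0.5 points, and the errors cancel when both arms are alike. It bounds the response from below in each arm, but does not correct the main estimate, and it is not a lower bound for the risk difference. Finally, Protocol 14.3.5.1 expects few discontinuations; q = 10% would mean about 7 of 69 and 2 of 23 subjects.

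**Conclusion.** The point holds as a modest weakness of one supplementary analysis. The written model omits both the early termination rating and off-IMP status, so stoppers without a Week 16 value are drawn at close to the on-treatment response of their arm.

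The figure of 0.8 to 1.6 points rests on an assumed 5 to 10% stopped and missing, equal shares and equal off-drug response in both arms, and the adult phase 3 rates. The direction is not guaranteed: more missing stoppers on vehicle can cancel the bias. The CMH companion analysis in SAP 5.6.1.4 uses the same imputation and shares the weakness. The improvement is worth making because it is cheap, not because a decision depends on it.

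**What to change.** Add a rule to SAP 5.1.1.1.1, and a matching data step before the PROC MI call in 7.2.1:

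- When IMP is stopped before Week 12, the early termination IGA-CHE is entered as the value of the first unobserved scheduled visit at or after the stop, up to and including Week 12 (W30 to W60 only).
- It is never carried into Week 16 (W70). If Week 16 is missing, it stays missing and is imputed.

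If the ADRG already holds such a rule, state it in the SAP. The note under the code also needs correcting, since it names IGABL and w1, which the code does not contain.

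Cost: a few lines of text and code before unblinding, with no new data and no change to MAR within treatment group. The nominal week will differ slightly from the actual date. For stops before Week 4, the rating reaches the Week 16 model only through the imputed Weeks 8 and 12. Only part of the bias is removed.

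A pooled-arm on/off-IMP indicator need not be required. The code runs separately by arm, so the indicator would mean restructuring the imputation, and with 23 vehicle subjects and few returners it may be barely estimable. Keep the non-response analysis in SAP 5.6.1.3 as the lower bound per arm.
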